9.3 On IP treatment

Registered subjects will be treated with talimogene laherparepvec based on lesion size, administered at of 10⁶ (1 million) PFU/mL administered intralesionally for the first visit and 10⁸ (100 million) PFU/mL administered intralesionally for subsequent visits (V2-4). A full description of treatment plan and dosing is outlined in sections 2.4 and 7.1.

Visit 1- First injection visit (7 - 28 days +/- 3 days)

- Skin exam only of target lesions
- Review of all blood work and confirmation to continue in the study
- Review of the biopsies of SCC lesions to confirm SCC diagnosis
- Assess adverse events
- Assess con med changes
- Complete inclusion/exclusion criteria
- Assign subject study number starting with SCC-01 and continue to be assigned sequentially
- Vital signs
- Photograph and measure all target lesions (Appendix A)
- Inject TILs
- Provide patient education on any side effects to expect and the treatment of the injected sites
- Schedule the next injection visit in 3 weeks

Visit 2- Second injection visit (21 days +/- 3 days)

- Vital signs
- Review con meds
- Assess for any adverse events
- Skin exam only of target lesions
- Photograph and measure all target lesions (Appendix A)
- Inject TILs
- Provide patient education on any side effects to expect and the treatment of the injected sites
- Schedule the next injection visit in 2 weeks

Visit 3- Third injection visit (14 +/- 3 days)

- Vital signs
- Review con meds

- Assess for any adverse events
- Skin exam only of target lesions
- Photograph and measure all target lesions (Appendix A)
- Inject TILs
- Provide patient education on any side effects to expect and the treatment of the injected sites
- Complete bloodwork (CBC, CMP)
- Schedule the next injection visit in 2 weeks.

Visit 4- Fourth injection visit (14 +/- 3 days)

- Vital signs
- Review con meds
- Assess for any adverse events
- Skin exam only of target lesions
- Photograph and measure all target lesions (Appendix A)
- Inject TILs
- Provide patient education on any side effects to expect and the treatment of the injected sites
- Schedule the first follow up visit in 4 weeks.

Visit 5- First follow up visit (28 +/- 7 days)

- Vital signs
- Review con meds
- Assess for any adverse events
- Skin exam only of target lesions
- Photograph and measure all target lesions (Appendix A)
- Schedule the second follow up visit in 4 weeks

Visit 6- Second follow up visit (28 +/- 7 days)

- Vital signs
- Review con meds

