9.4.1.1 Tumor Response

Complete Response (CR): Complete disappearance of all TILs (whether measurable or not, and no new lesions at the site of injection) confirmed by an assessment 8 weeks after the end of the injections (Visit 6).

Partial Response (PR): Decrease in tumor burden $\ge 30\%$ relative to baseline confirmed by an assessment 8 weeks after the end of the injections (Visit 6).

Duration of Overall Response (DOR): DOR is when the time measurement criteria are met for CR or PR (whichever status is recorded first) until the first date that recurrence or progressive disease (PD) is objectively documented, taking as reference for PD the smallest measurements recorded since the treatment started. If no recurrence or PD is documented after PR or CR is observed the time measurement will be performed at Visit 6 for PR and Visit 8 for CR.

Durable Response Rate (DRR): Measured from the time measurement criteria are met for CR or PR (whichever status is recorded first) with the response lasting continuously for > than or equal to 6 months. For PD, the reference will be the
smallest measurements recorded since the treatment started.

Time to progression (TTP): This will be measured from the time treatment is initiated until the first date that recurrence or progressive disease (PD) is objectively documented, taking as reference for PD the smallest measurements recorded since the treatment started.

Progressive Disease (PD): Progression is defined as >20% increase of at least 5 mm in the sum of the longest diameters of the target lesions or increase in tumor burden $\ge 20\%$ relative to nadir (minimum recorded tumor burden) or the appearance of one or more new lesions confirmed by an assessment 8 weeks after the end of the injections (Visit 6).

• **Rapid PD (RPD):** Is defined as an increase of >50% in tumor burden for lesions >2 cm in diameter or 100% tumor burden increase for lesion ≤2cm between visits.

Stable Disease (SD): Not meeting criteria for CR or PR, in absence of PD (Decrease of tumor size <30% to increase in size <20% of less than 5 mm in the sum of the longest diameters of the target lesions).

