9.5.1 Follow up

Visit 5- First follow up visit (28 +/- 7 days)

- Vital signs
- Review con meds
- Assess for any Adverse Events
- Skin exam limited to all target lesions
- Photograph and measure target lesions (Appendix A)
- Schedule the next follow up visit in 4 weeks.

Visit 6- Second follow up visit (28 +/- 7 days)

- Vital signs
- Review con meds
- Assess for any Adverse Events
- Skin exam limited to all target lesions
- Photograph and measure target lesions (Appendix A)
- Schedule second ultrasound to be completed on TILs before next follow up visit
- Schedule the next follow up visit in 6 weeks.

Visit 7- Third follow up visit (42 +/- 10 days)

- Vital signs
- Review concurrent meds

- Assess for any Adverse Events
- Skin exam limited to all target lesions
- Photograph and measure target lesions (Appendix A)
- Schedule the next follow up visit in 14 weeks.

Visit 8 - Fourth follow up visit (98 +/- 21 days)

- Vital signs
- Review con meds
- Assess for any adverse events
- Skin exam limited to all target lesions
- If sites are free of disease, participant participation will be complete
- Photograph and measure target lesions (Appendix A)
- Complete subject payment form

Visit 9 – Telephone Follow up (356 +/- 31 days) after Visit 1

• Assess for changes of target lesions

• If active lesion(s) are noted by the participant, they will follow up with a dermatologist and their records will be requested

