16. STATISTICAL CONSIDERATIONS

16.1 Analysis Endpoints

16.1.1 Primary Endpoint

The primary end point is to evaluate the overall response rate (ORR) defined as proportion of subjects who achieved CR and PR in the cSCC TILs. Clinical assessments will be done using a ruler or calipers. Digital photograph of the lesion(s) will be recorded each visit. Through clinical evaluation, CR will be defined as the complete disappearance of all TILs and PR will be defined as at least a 30% decrease in the sum of the diameters of TILs, taking as reference the baseline sum diameters. Progression is defined as >20% increase of at least 5 mm in the sum of the longest diameter recorded or increase in tumor burden \ge 20% relative to nadir (minimum recorded tumor burden) or the appearance of recurrent lesions confirmed by an assessment 8 weeks after the end of the injections (Visit 6). Stable disease (SD) is defined as decrease in tumor size <30% or an increase in size <20%.

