- A sum of the longest diameter (LD) will be calculated and reported as the baseline sum LD for *both TILs and TNILs respectively*. The baseline sum LD will be used as reference by which to characterize the objective tumor.

Response Criteria:

Complete Response (CR):	Disappearance of all TILs
Partial Response (PR):	At least a 30% decrease in the sum of the LD of TILs, taking as reference the baseline sum LD
Progressive Disease (PD):	 >20% increase of at least 5 mm in the sum of the longest diameters of the target lesions Or increase in tumor burden ≥ 20% relative to nadir (minimum recorded tumor burden) Or the appearance of one or more new lesions confirmed by an assessment 8 weeks after the end of the injections (Visit 6).
Stable Disease (SD):	A decrease in tumor size <30% or an increase in size <20% that is less than 5 mm in the sum of LDs of the TILs compared with the smallest sum of the LD recorded.

Evaluation of TILs

Evaluation of TNILs

Complete Response (CR):	Disappearance of all TNILs
Partial Response (PR):	At least a 30% decrease in the sum of the diameters of TNILs, taking as reference the baseline sum LD
Progressive Disease (PD):	 >20% increase of at least 5 mm in the sum of the longest diameters of the target lesions Or increase in tumor burden ≥ 20% relative to nadir (minimum recorded tumor burden) Or the appearance of one or more new lesions confirmed by an assessment at Visit 3.
Stable Disease (SD):	A decrease in tumor size <30% or an increase in size <20% that is less than 5 mm in the sum of LDs of the TNILs compared with the smallest sum of the LD recorded.

Evaluation of best overall response

The best overall response is the best response recorded from the start of the treatment until disease progression/recurrence (taking as reference for PD the smallest measurements recorded since the treatment started). In general, the patient's best response assignment will depend on the achievement of both measurement and confirmation criteria

TILs	TNILs	Recurrent TILs	Overall response
CR	CR	No	CR
CR	Incomplete response/SD/PD	No	CR
PR	Any	No	PR
SD	Any	No	SD
PD	Any	Yes or No	PD

Patients with a global deterioration of health status requiring discontinuation of treatment without objective evidence of disease progression at that time should be classified as having "symptomatic deterioration". Every effort should be made to document the objective progression even after discontinuation of treatment.

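### Subject-level progression counts any new lesion in 9.4.1.1 and Appendix B but only recurrent lesions in the primary endpoint, so one subject can meet both response and progression

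*Combined protocol and SAP*

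**What the plan says.** Subject-level response is defined in three places.

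- **Section 9.4.1.1.** Complete response (CR) is "Complete disappearance of all TILs (whether measurable or not, and no new lesions at the site of injection", confirmed at Visit 6. Partial response (PR) is a fall of at least 30% from baseline, with no mention of new lesions. Progressive disease (PD) is met by either of two growth limbs, "or the appearance of one or more new lesions confirmed by an assessment 8 weeks after the end of the injections (Visit 6". Only stable disease (SD) is conditional on PD being absent.
- **Section 16.1.1 (primary endpoint).** CR and PR rest on the TILs alone. The last PD limb is different: "or the appearance of recurrent lesions confirmed by an assessment 8 weeks after the end of the injections (Visit 6".
- **Appendix B.** The TIL criteria return to the wide form: "Or the appearance of one or more new lesions confirmed by an assessment 8 weeks after the end of the injections (Visit 6". The best-overall-response table in the same appendix has no new-lesion column. Its third column is "Recurrent TILs", and it gives CR when the TILs are CR and the non-injected lesions (TNILs) are "Incomplete response/SD/PD".

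Section 9.4.1 names the Appendix B criteria as those used to judge tumor response. No section says which definition prevails.

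After screening, the skin examination is narrow: "Skin exam only of target lesions" in 9.3 and "Skin exam limited to all target lesions" in 9.5.1.

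**The concern.** The trial turns on a count of responders, and under 9.4.1.1 and Appendix B the categories being counted overlap. A subject with cleared TILs and a new squamous cell carcinoma away from them satisfies CR and PD together. PR overlaps PD in the same way.

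The population makes this possible, since 1.2 admits people with multiple carcinomas. The study is single-arm, and 16.3 has stage 1 results evaluated as they accrue. A rule left open would therefore be settled with outcomes in view. PD is also the event for time to progression (TTP), duration of response (DOR) and durable response rate (DRR).

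Two smaller gaps touch the same definitions. Nothing says how a TIL withdrawn and treated otherwise before Visit 6 (Table 7 in 9.4.1.2) enters the Visit 6 assessment when the subject has other TILs. Tumor burden is never defined, which leaves the relation between the two PD growth limbs unclear.

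**Working it through.** **1. The plan's own figure.** Inputs from 16.2.1: null 50%, alternative 80%, 7 then 13 more subjects, continue on 5 or more of 7, succeed on 14 or more of 20.

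P(success | p) = sum over x = 5 to 7 of P(Bin(7, p) = x) × P(Bin(13, p) ≥ 14 − x).

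- p = 0.50: 0.0417, within the one-sided 0.05.
- p = 0.80: 0.8122, matching the stated 80% power.

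The design is sound. The question is what counts as a responder. One reclassified subject moves 5/7 (71.4%) to 4/7 (57.1%), or 14/20 (70%) to 13/20 (65%). It changes the decision only at those boundaries.

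**2. The definitions side by side**, for a subject with all TILs gone and a new lesion elsewhere:

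| Source | New-lesion bar on CR | Lesion limb of PD | Class |
|---|---|---|---|
| 9.4.1.1 | injection site only | any new lesion | CR and PD |
| Appendix B, TIL criteria | none | any new lesion | CR and PD |
| 16.1.1 | none | recurrent lesions | CR |
| Appendix B, best-response table | none | recurrent TILs | CR |

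Appendix B takes the best response up to progression or recurrence. That orders events at different visits. It does not settle a new lesion first seen at, or before, the visit that shows the response.

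**3. Effect on the time endpoints.** From the Table 1 intervals, in weeks from Visit 1: Visit 4 = 3 + 2 + 2 = 7; Visit 6 = 7 + 4 + 4 = 15; Visit 8 = 15 + 6 + 14 = 35. Suppose CR criteria are first met at Visit 4 and still met at Visit 6, the TILs stay clear to Visit 8, and a new lesion elsewhere is noted at Visit 6.

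- Any new lesion counts: TTP 15 weeks; DOR 15 − 7 = 8 weeks; not durable.
- Only recurrence counts: no TTP event by week 35; DOR to Visit 8 is 35 − 7 = 28 weeks, more than 6 months (about 26 weeks); durable.

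**4. Withdrawn TIL (illustrative sizes).** Baseline 20 + 15 mm; the first shrinks to 10 mm and the second is withdrawn at 24 mm.

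- Last value kept: 34/35, a 2.9% fall, no response.
- Dropped from both sums: 10/20, a 50% fall, PR.
- Counted as zero: 10/35, a 71.4% fall, PR.

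For m equal TILs with k withdrawn at w × baseline and the last value kept, PR needs the remaining TILs at or below (0.7m − wk)/(m − k) of baseline. With m = 2, k = 1:

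- w = 0.6: 0.80, a 20% fall is enough.
- w = 0.7: 0.70, a 30% fall, the same as dropping the lesion.
- w = 1.0: 0.40, a 60% fall is needed.

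Because PD is measured from nadir, withdrawal below 0.7 × baseline is possible (nadir 0.5, then 0.5 × 1.2 = 0.6). Carrying the value forward then makes PR easier.

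**5. Growth limbs.** Assume tumor burden means the sum of diameters. Since nadir cannot exceed baseline, a rise of more than 20% and at least 5 mm always also meets the limb of 20% or more over nadir, so the 5 mm limb adds nothing. For any nadir sum below 5/0.20 = 25 mm, less than 5 mm of growth is enough (20 mm: 4 mm; 10 mm: 2 mm). SD carries a 5 mm condition in 9.4.1.1 and Appendix B but not in 16.1.1.

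**The case against.** The strongest reply is that the primary count is already settled in substance. Response is defined on TILs in 1.3, 3.1 and 16.1.1. The only rule that combines the categories, the best-response table, is keyed to TIL status. It keeps CR despite TNIL progression, which in Appendix B itself includes new lesions. TTP, DOR and DRR are likewise labelled as endpoints of the TILs. Most of this stands, and it is why the effect on the primary count is judged small. It remains an inference: no section states precedence, and 9.4.1 points to criteria whose PD line says otherwise.

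A second reply is that the wide clause needs confirmation at Visit 6, where the examination covers target lesions only. That limits exposure but does not remove it. Regional photographs of the anatomical area and adverse event review also take place at Visit 6, so a remote lesion can come to notice, though unsystematically. The 9.4.3 chart review spans the 8 weeks from Visit 4 to Visit 6, but it is exploratory and nothing feeds it into PD.

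A reader might infer from step 5 that the 5 mm condition ought to be made to operate. The documents do not support that choice. The nadir limb appears in 9.4.1.1, 9.4.1.2, 16.1.1 and Appendix B, joined by an or; redundancy does not show which limb was meant.

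**Conclusion.** The concern holds as an inconsistency in the definition of subject-level PD. Under 9.4.1.1 and the Appendix B TIL criteria, a subject with responding TILs and a new lesion elsewhere is both responder and PD. Under 16.1.1 the subject is a responder.

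The likely effect on the primary count is small. It depends on how often such lesions are seen, which the documents do not give, and it alters the decision only at 5 versus 4 of 7 or 14 versus 13 of 20. The effect on TTP, DOR and DRR is more direct, as step 3 shows for one subject.

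A reader might infer a serious loss of power. If 5%, 10% or 20% of responders were rescored as PD, a true 80% rate would give power of 69.7%, 56.1% or 29.4%. Those shares are assumptions without a source, and the calculation scores such subjects against 16.1.1 and the best-response table. No change in error rate is claimed.

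The withdrawn-TIL gap concerns only subjects with more than one TIL, one of which is withdrawn before Visit 6. The growth-limb point rests on reading tumor burden as a sum of diameters.

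**What to change.** For endpoint scoring only:

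1. Use the 16.1.1 rule for subject-level PD in 9.4.1.1 and the Appendix B TIL criteria: growth or recurrence of the TILs, with a new lesion at the injection site included. State that a new lesion away from the TILs does not alter TIL response, TTP, DOR or DRR.
2. List such lesions descriptively when existing sources (adverse events, photographs, chart review) show them. Add no examinations.
3. State that a TIL withdrawn and given alternative treatment before Visit 6 cannot count as disappeared, and is a non-responding lesion in the lesion-level rate of 16.1.2. Carry its last measurement before alternative treatment into the Visit 6 sum. Because this can ease the PR threshold below 0.7 × baseline, add a sensitivity analysis that scores such subjects as non-responders.
4. Define tumor burden, and have the sponsor reconcile the two growth limbs and the SD wording across 9.4.1.1, 16.1.1 and Appendix B. No choice between the limbs is proposed.

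Lesion-level PD in 9.4.1.2 and Table 7 carries the same new-lesion clause and governs lesion management. It must be reconciled with the revised definitions; no clinical rule is proposed.

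Cost: wording and one small analysis, with sample size and cut-offs unchanged. Downside: TTP and DOR may look slightly more favourable than if every new lesion counted, and the listing in item 2 will be incomplete.

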9.4.1.2 Clinical Management of TILs and TNILs

Along with assessing the overall tumor response (see Section 9.4.1.1, Tumor Response), each individual lesion will be assessed to determine appropriate clinical management. The RECIST 1.1 (Appendix B) response criteria will also be used to evaluate each individual tumor response.

Individual Lesion Complete Response (IL-CR): Complete disappearance of target lesion (whether measurable or not, and no new lesion(s) at the site of the target lesion) confirmation by an assessment 8 weeks after the end of the injections (Visit 6).

Individual Lesion Partial Response (IL-PR): Decrease in tumor burden $\ge 30\%$ relative to baseline confirmed by an assessment 8 weeks after the end of the injections (Visit 6).

Individual Lesion Progressive Disease (IL-PD): Progression is defined as >20% increase of at least 5 mm in the sum of the longest diameters of the target lesions or increase in tumor burden $\ge 20\%$ relative to nadir (minimum recorded tumor burden) or the appearance of one or more new lesions confirmed by an assessment 8 weeks after the end of the injections (Visit 6).

 Individual Lesion Rapid PD (IL-RPD): Is defined as an increase of >50% in tumor burden for lesions >2 cm in diameter or 100% tumor burden increase for lesion ≤2cm between visits.

Individual Lesion Stable Disease (IL-SD): Not meeting criteria for CR or PR, in

absence of PD (Decrease of tumor size <30% to increase in size <20% of less than 5 mm in the sum of the longest diameters of the target lesions).

	Individual Lesion	Individual	Progressive Disease	Stable Disease
	Complete Response	Lesion Partial	(PD)	(SD)
	(IL-CR)	Response (IL-		
	IL-CR to be	PR)		
	determined at the latest by Visit 6 (8	 IL-PR will be followed and assessed at 	 If IL-PD confirmed in two consecutive visits OR at Visit 6 (8 week 	 IL-SD will be followed and assessed up to
	week follow up), and will be followed for 6	assessed at Visit 6 (8 week follow up)	OR at Visit 6 (8 week follow up), TIL will be withdrawn and	assessed up to Visit 6 (8 week follow up)
	months • No additional	 If IL-SD is documented at 	alternative therapeutic intervention given	 Alternative therapeutic

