16.1.2 Secondary Endpoints

 To assess the safety and adverse effect profile of talimogene laherparepvec in low risk cSCC. Adverse events to be assessed according to National Cancer Institute Common Terminology. This will be determined by incidence of all adverse events (AEs), grade ≥ 3 AEs, safety adverse events (SAEs), and events requiring the discontinuation of study drug, local effects on the tumor (ie, pain, inflammation and ulceration), and any clinically significant laboratory values.

- 2. Time to response in cSCC TILS. Time to response is the time from first visit until objective tumor response (CR or PR) is identified
- 3. Duration of overall response (DOR) of TILs. This will be measured from the time measurement criteria are met for CR or PR (whichever status is recorded first) until the first date that recurrence or progressive disease (PD) is objectively documented, taking as reference for PD the smallest measurements recorded since the treatment started. If no recurrence or PD is documented after PR or CR is observed the time measurement will be performed at Visit 8.
- 4. Durable response rate of TILs. The duration of overall response is ORR lasting continuously for > than or equal to 6 months.
- 5. Time to progression (TTP) of TILs. This will be measured from the time treatment is initiated until the first date that recurrence or progressive disease (PD) is objectively documented, taking as reference for PD the smallest measurements recorded since the treatment started.
- 6. Overall response rate (CR+PR) of TILs assessed by imaging technique (high frequency ultrasound) and correlate it with clinical overall response rate.
- 7. Overall clinical response rate (CR+PR) of individual TILs injected with talimogene laherparepvec (not as overall subject response). Overall response rate is defined as the proportion of injected lesions which achieved complete and partial response.

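### The Visit 6 confirmation clause in the progression definition does not fit TTP and DOR, which run to Visit 8: new lesions after Visit 6 or in subjects withdrawn before it cannot count, and relapse is ambiguous

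*Combined protocol and SAP*

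**What the plan says.** **Definition of PD.** Section 9.4.1.1 gives three alternatives joined by *or*. The first is growth: "Progression is defined as >20% increase of at least 5 mm in the sum of the longest diameters of the target lesions". The second is a rise in tumor burden of at least 20% from nadir. The third is "or the appearance of one or more new lesions confirmed by an assessment 8 weeks after the end of the injections (Visit 6". Appendix B repeats the three for TILs. Section 16.1.1 replaces new lesions with recurrent ones: "the appearance of recurrent lesions confirmed by an assessment 8 weeks after the end of the injections (Visit 6". For non-injected lesions (TNILs), Appendix B names Visit 3 instead.

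**Where PD is used.** Section 16.1.2 defines TTP: "This will be measured from the time treatment is initiated until the first date that recurrence or progressive disease (PD) is objectively documented". Section 9.4.1.1 ends DOR in the same terms: "until the first date that recurrence or progressive disease (PD) is objectively documented". Durable response is defined as response "with the response lasting continuously for > than or equal to 6 months".

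**End of DOR when no event occurs.** In section 9.4.1.1, "the time measurement will be performed at Visit 6 for PR and Visit 8 for CR". Section 16.1.2 gives Visit 8 for both.

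**Lesion-level rule.** Table 7 in section 9.4.1.2 acts on a progressing TIL under a different rule, "If IL-PD confirmed in two consecutive visits" or at Visit 6. It withdraws a subject whose only TIL progresses.

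**The concern.** Visit 6 is the natural time to classify response for the primary endpoint. The same definition of PD, with its fixed visit, is then reused for endpoints that continue well beyond it. An assessment at Visit 6 cannot confirm something first seen at Visit 7 or 8, and a subject who leaves before Visit 6 has no such assessment.

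If the wording is applied as written, some genuine progressions are not events, and TTP and DOR look longer than they are. If it is applied loosely, two analysts can code the same subject differently and both can cite the plan.

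**Working it through.** **1. The plan's own figure.** The only design calculation is the Simon rule in section 16.2.1: continue with at least 5 responders of 7, and call the treatment promising with at least 14 of 20. The probability of success at response rate p is the sum over x = 5, 6, 7 of P(x responders of 7) × P(at least 14 − x responders of 13).

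- p = 0.5: alpha 0.0417 (limit 0.05)
- p = 0.8: power 0.812 (stated 80%)

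The stated design is reproduced. It uses response only, so the PD wording after Visit 6 does not enter it.

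**2. Timeline.** The visit intervals in section 2.4 are 3, 2, 2, 4, 4, 6 and 14 weeks.

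| Visit | 1 | 2 | 3 | 4 | 5 | 6 | 7 | 8 |
|---|---|---|---|---|---|---|---|---|
| Week | 0 | 3 | 5 | 7 | 11 | 15 | 21 | 35 |

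Time after Visit 6 is 35 − 15 = 20 weeks, and 20/35 = 57% of the in-person follow-up for TTP. This is not a fraction of DOR, which starts at response.

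**3. Durable response.** The earliest post-baseline measurement is at week 3. Adding six months, about 26 weeks, gives week 29. Every decision that a response was durable therefore falls after Visit 6.

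**4. Early withdrawal.** Under the consecutive-visit rule in Table 7, the earliest pair of post-baseline visits is Visits 2 and 3. A subject with one TIL can therefore be withdrawn at Visits 3 to 5 (weeks 5 to 11). Section 16.2 keeps every treated subject in the efficacy analysis, but no section says how PD is confirmed for a subject who has left.

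**5. The definitions applied case by case.** The narrow reading attaches the Visit 6 clause only to the last limb. The broad reading attaches it to the whole sentence.

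| Case | PD, narrow reading | PD, broad reading | Event as recurrence? |
|---|---|---|---|
| New lesion first seen at Visit 7 or 8 | No | No | Unclear, term undefined |
| Reappearance at Visit 7 or 8 after all TILs had cleared | No | No | Yes by 9.4.1.1 and 16.1.2; but 16.1.1 puts recurrent lesions inside Visit 6-bound PD |
| Growth of a remaining TIL at Visit 7 or 8 | Yes | No | Not applicable |
| Growth leading to withdrawal at Visits 3 to 5 | Yes | No | Not applicable |
| New lesion in a subject withdrawn before Visit 6 | No | No | Unclear |

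In the second row the nadir is zero, so a percentage increase cannot be computed and the growth limbs do not help.

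The two new-lesion rows fail on either reading. The two growth rows depend on the reading, and the relapse row depends on the section consulted.

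**The case against.** The strongest reply is that TTP and DOR end at recurrence *or* PD. Recurrence is listed separately and carries no visit limit, and Table 7 responds to recurrence at any time after a complete response. Regrowth of a cleared lesion at Visit 7 or 8 can then end TTP or DOR without meeting the definition of PD. This stands as far as it goes. A reader might infer that every relapse after Visit 6 is lost, and the documents do not support that. What remains is that recurrence has no definition of its own, and the statistical section places recurrent lesions inside the limb tied to Visit 6.

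Second, Appendix B sets out the limbs as separate items, with the visit attached only to new lesions. That favours the narrow reading, under which growth before withdrawal does count. Against it, section 9.4.1.1 applies the same clause to the whole of CR and of PR, and Appendix B makes best response depend on confirmation as well as measurement. The text does not settle the question. It would therefore be too strong to say that all progression in withdrawn subjects is lost.

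Third, durable response requires unbroken response, and section 9.4.1.1 brings PD into it only through the nadir reference. This is correct. Durable response is affected only to the extent that loss of response is judged by the same criteria.

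Fourth, a reader might assume that 10% to 30% of responders relapse after Visit 6 and infer a bias of 10 to 30 points. That only restates the assumption, and it also treats every recurrence as uncounted. The documents give no relapse or new-lesion rate, and the skin examinations at Visits 7 and 8 are limited to target lesions.

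**Conclusion.** The point holds for new lesions. On the literal wording, those first seen at Visit 7 or 8, or in a subject withdrawn before Visit 6, cannot be PD. For relapse after Visit 6 the plan gives conflicting answers. Growth before withdrawal, or after Visit 6, is lost only on the broad reading.

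Any error is toward longer TTP and DOR. Its size cannot be derived from the documents. As a scale only, if 14 responders (the success threshold) were all still at risk, one uncounted event would move the Kaplan-Meier curve for DOR by 1/14, about 7 points. With 20 responders it would be 1/20, or 5 points.

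The primary response rate is assessed at Visit 6, and neither it nor the Simon design changes. The affected endpoints are secondary and carry no hypothesis test. This should be fixed, but it does not threaten the primary conclusion.

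**What to change.** - Keep Visit 6 as the time of the primary response classification only.
- For TTP and DOR, and for loss of response in the durable response rate, remove the Visit 6 clause from PD in sections 9.4.1.1 and 16.1.1 and in Appendix B.
- Define recurrence once and use that definition throughout.
- Date PD or recurrence at the first visit at which it is objectively documented, through Visit 8.
- If confirmation is required, exempt events first seen at Visit 8. The only later contact is the Visit 9 telephone call, so a next-visit rule would recreate the problem there.
- Count progression that led to withdrawal before Visit 6 as an event.
- Reconcile these definitions with the Table 7 rule, with the Visit 3 clause for TNILs in Appendix B, and with the end of DOR for partial responders (Visit 6 in section 9.4.1.1, Visit 8 in section 16.1.2). Which management rule in Table 7 is right is not judged here.

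The cost is wording. Lesions are already measured at every in-person visit and at the early termination visit, so no new data are needed, and sample size, alpha and power do not change. Reported durations may be slightly less favourable.
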